#### 16.11 Primary Endpoint

The primary endpoint for this study is overall response rate (ORR) at 36 weeks after registration, which is defined as the percentage of patients, among evaluable patients, who experience an objective response within 36 weeks. Objective response is defined as a complete or partial response per RECIST 1.1, without the confirmation scan. The evaluable patients are those who are eligible, consented, received any protocol treatment, and are not major violations.

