## 4.0 Test Schedule

### 4.1 Schedule of Assessments

Tests and Procedures	Screening	Active Monitoring					
		Cycle 1			Cycles 2 +	End of Treatment	Safety 
	Days -28 to -1	Day 1 	Day 8 ±3 days 	Day 15 ±3 days 	Day 1 ±3 days 	Last day of treatment +14 days 	EOT +30-35 days
COLOMATE Companion Trial Recommendation Form(optional) 	X						
Demography and medical history	X						
Hepatitis B and C screening	X						
Vital Signs, ECOG performance status 	X	X	X	X	X	X	X
Physical exam, weight, height	X	X	X	X	X	X	X
Review AEs	X	X	X	X	X	X	X
Review prohibited meds 	X	X	X	X	X	X	X
Review patient medication diary			X	X	X	X	
Eye examination R	X				X  (every 3 cycles starting with c3d1)	X	

Tests and Procedures	Screening	Active Monitoring					
		Cycle 1			Cycles 2 +	End of Treatment	Safety 
	Days -28 to -1	Day 1 	Day 8 ±3 days 	Day 15 ±3 days 	Day 1 ±3 days 	Last day of treatment +14 days 	EOT +30-35 days
CT or MRI 	X				X  (Restaging at end of cycles 3, 6, 9 etc.)	X 	
12-lead ECG 	X	X		X	X	X	X
Hematology and Serum Chemistries	X	X	X	X	X	X	X
Tumor Blood Biomarkers (CEA) 	X 	X			X		
Coagulation panel	X				X  (day 1 of c4, 7, 10 etc.)	X	
Parathyroid hormone (PTH) R	X	X			X	X	
Lipid panel R		X				X	
Mandatory Patient Questionnaire Booklet (Appendix V) 		X			X	X	
Urinalysis	X				X  (day 1 of c4, 7, 10 etc.)		

Tests and Procedures	Screening	Active Monitoring					
		Cycle 1			Cycles 2 +	End of Treatment	Safety 
	Days -28 to -1	Day 1 	Day 8 ±3 days 	Day 15 ±3 days 	Day 1 ±3 days 	Last day of treatment +14 days 	EOT +30-35 days
Pregnancy test 	X 	X			X	X	
Blood sample-cfDNA Guardant360 (optional) 13,R						X	
Mandatory archival tissue 8,R	X						
Mandatory blood sample plasma 9,R		X			X  (c2d1; then on d1 following restaging scans (c4, 7, 10, etc.))	X	
Mandatory blood sample- Whole blood R		X 					

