**Notes:**

R Research funded (see Section 19).

1. If the subject is participating through the COLOMATE platform: The COLOMATE Companion Trial Recommendation Form must indicate that the patient has met molecular eligibility to screen. The patient must be registered to the companion study ≤30 days from date of COLOMATE Companion Trial Recommendation Form completion. If the COLOMATE Companion Trial Recommendation Form recommends a different companion study, patient may still enroll after approval by the study PI or designee. Form must be uploaded to supporting documentation folder in RAVE.

2. Vital Signs: Including heart rate, blood pressure and temperature (oral or tympanic) and ideally performed with subject in a recumbent or semirecumbent position after 5 minutes of rest.
3. Prohibited Medications: List of prohibited medications in section 9.11 should be reviewed at study entry and during treatment.
4. Comprehensive Eye Examination: To be performed by a qualified ophthalmologist at screening, once every 3 cycles starting with Cycle 3, Day 1 ( $\pm 14$  days); at EOT, and as clinically indicated. The eye examination should include a visual acuity test, slit-lamp examination, OCT, and funduscopy with digital imaging. Additional assessments should be performed if clinically relevant retinal findings are observed on ophthalmologic exams and in participants with reported visual AEs or change in visual acuity, if the events or changes are suspected to be of retinal origin. Every effort should be made to ensure that all subsequent examinations are performed by the same ophthalmologist.
5. Computed Tomography (CT) / Magnetic Resonance Imaging (MRI): Baseline evaluation of disease status by CT or MRI completed  $\leq 28$  days prior to registration. Baseline and subsequent scans to include imaging of the primary site of disease plus any additional sites of known or suspected disease. Re-scanning to occur every 9 weeks (minus 1-6 days) after initiating protocol treatment on Cycle 1, Day 1. (The minus 1-6 day scan window is intended for flexibility in scheduling re-scans during Week 3 of every 3rd cycle – i.e. re-scanning intended between Days 15-21 of Cycles 3, 6, 9, etc.)  

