Same-day scanning on Day 1 of Cycles 4, 7, 10, etc. is discouraged but allowed, provided scan results receive appropriate RECIST review prior to initiating/continuing Pemigatinib in the new cycle of study treatment (e.g. first re-scan is discouraged, but permitted on Cycle 4, Day 1, provided RECIST review occurs prior to dispensing Pemigatinib for Cycle 4).  
CT/MRI required at EOT only if it has been  $>28$  days since the previous CT/MRI.
6. Electrocardiogram (ECG): Single trace 12-lead ECGs on site equipment ideally performed with subject in a recumbent or semirecumbent position after 5 minutes of rest. ECGs will be interpreted locally by the site and used for subject management. Management decisions (e.g. include or exclude a subject or withdraw a subject from the study) based on an ECG finding such as "Abnormal, Clinically Significant" is the responsibility of the investigator, in consultation with the sponsor-investigator, as appropriate. Clinically notable abnormalities considered clinically significant by the investigator are to be reported as AEs.
7. Pregnancy Test: For all women of childbearing potential (WOCBP) – as defined in Appendix I – serum pregnancy test required during screening; and serum or urine pregnancy test to be conducted on Day 1 of Cycle 1 (before first dose of Pemigatinib), on Day 1 of every cycle, at the EOT visit, and additionally as medically indicated. If a urine pregnancy test is positive, the results should be confirmed with a serum pregnancy test: If the serum pregnancy test is negative after a urine test was positive, the investigator will assess the potential benefit/risk to the subject and determine whether it is in the subject's best interest to resume study drug and continue participation in the study.

8. Archival Tissue: Receipt of archival tumor tissue is not required for study registration and initiation of therapy. However, it is mandatory to receive the required tissue within 90 days from randomization. See section 17.0.
9. Mandatory Blood Sample-Plasma: Mandatory collection on Day 1, cycle 1; day 1, cycle 2; and on day 1 of each cycle which is immediately following radiographic assessment for re-staging ( day 1 of cycles 4,7,10, etc.) and at EOT (see Section 14). Kits required for collection. Patient must be registered prior to collection.

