10. Administrative Scheduling Window: After Cycle 1, Day 1, allowance of  $\pm 3$  days for subsequent study visits is permitted for scheduling considerations other than adverse event management (e.g. holidays, weekends, inclement weather).
11. End-of -Treatment (EOT): Reasonable effort should be made to complete End-of-Treatment (EOT) procedures on the day it is decided a patient will no longer receive Pemigatinib. These procedures must be completed subsequent to and not later than 14 days after investigator decision to permanently discontinue Pemigatinib and prior to any subsequent anti-cancer therapy. CT/MRI required at EOT only if it has been  $>28$  days since the previous CT/MRI.
12. Safety Follow-Up: One-month follow-up (1M F/U) visit to be performed 30 to 35 days after the EOT visit. (In the event EOT visit not performed, then the safety follow-up visit is to be performed 30-35 days after the last dose of Pemigatinib.) Any adverse event in the Safety Follow-up will be recorded on the adverse event assessment form in the last cycle of treatment. The Safety Follow-up is recommended by the study protocol, but no data collection is required other than adverse event assessment.
13. Patients have the option to complete cfDNA testing at study completion and will be allowed to re-register with protocol ACCRU-GI-1611. Site will access results by creating an account at [REDACTED]. Sites will be notified by Guardant Health via email when results are available in the portal. See section 13.8. See detailed instructions on the ACCRU website under Manuals and Forms. Kits are required for this collection.
14. If screening tests occur  $\leq 3$  days prior to C1 D1, they do not have to be repeated prior to dosing.
15. Coagulation Panel: to be done at screening, restaging (day 1 of cycles 4, 7, 10 etc.) and end of treatment.
16. Urinalysis: to be done at screening and restaging (day 1 of cycles 4, 7, 10, etc.).
17. Mandatory blood sample-Whole blood: May occur prior to treatment on cycle 1 day 1. Refer to section 14.0
18. Tumor Blood Biomarkers (CEA): to be done  $\leq 7$  days prior to registration, and day 1 of every cycle thereafter.

19. Patient questionnaire will be completed at baseline, day 1 of each cycle, and end of treatment (within 30 days of last dose as noted in appendix V). Patient questionnaire booklets must be used; copies are not acceptable for this submission. The booklet order form is located on the ACCRU website under Manuals and Forms.

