#### Optional

An optional correlative research component is part of this study. There will be an option to select if the patient is to be registered onto this component (see Section 14.0).

- Patient has/has not given permission to give his/her blood sample for research testing.

6.13 Documentation of IRB approval must be on file in the Registration Office before an investigator may register any patients. Approvals should be uploaded using the online ACCRU Regulatory Management System (ARMS).

In addition to submitting initial IRB approval documents, ongoing IRB approval documentation must be on file (no less than annually) with ACCRU. Approvals should be uploaded using the online ACCRU Regulatory Management System (ARMS). If the necessary documentation is not submitted in advance of attempting patient registration, the randomization will not be accepted and the patient may not be enrolled in the protocol until the situation is resolved.

Submission of annual IRB approvals is required until the study has been closed through your IRB.

6.14 Prior to accepting the registration/randomization, the registration/randomization application will verify the following:

- IRB approval at the registering institution
- Patient eligibility
- Existence of a signed consent form
- Existence of a signed authorization for use and disclosure of protected health information

6.15 At the time of registration, the following will be recorded:

- Patient has/not given permission to store and use his/her blood sample(s) for future research to learn about, prevent, or treat cancer.
- Patient has/not given permission to store and use his/her blood sample(s) for future research to learn, prevent, or treat other health problems (for example: diabetes, Alzheimer's disease, or heart disease).
- Patient has/not given permission to store and use his/her tissue sample(s) for future research to learn about, prevent, or treat cancer.
- Patient has/not given permission to store and use his/her tissue sample(s) for future research to learn, prevent, or treat other health problems (for example: diabetes, Alzheimer's disease, or heart disease).
- Patient has/not given permission for ACCRU to give his/her sample(s) to outside researchers.

6.16 Treatment cannot begin prior to registration and must begin  $\leq$ 10 days after registration.

6.17 Pretreatment tests/procedures (see Section 4.0) must be completed within the guidelines specified on the test schedule.

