#### 16.2 Statistical Design

##### 16.21 Decision Rule

A Simon two-stage minimax design will be used. The largest success proportion where the proposed treatment regimen would be considered ineffective in this population is 5%, and the smallest success proportion that would warrant subsequent studies with the proposed regimen in this patient population is 20%. The following two-stage design uses 12 or 21 evaluable patients to test the null hypothesis that the true success proportion in this given patient population is at most 5%.

NOTE: We consider a success to be a patient with an objective response by 36 weeks post-registration (i.e. complete response or partial response).

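### The 36-week response cut is counted from registration but scans are counted from Cycle 1 Day 1, so an on-schedule fourth scan can fall outside the endpoint window (minor; wording fix)

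*Combined protocol and SAP*

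**What the plan says.** **Endpoint clock.** Section 16.11: "The primary endpoint for this study is overall response rate (ORR) at 36 weeks after registration"; 16.311 repeats this. The NOTE in 16.21 applies it to the decision rule: "We consider a success to be a patient with an objective response by 36 weeks post-registration".

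**Treatment start.** Section 6.16: "Treatment cannot begin prior to registration and must begin" no later than 10 days after registration.

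**Scan clock.** Section 4.1, note 5: "Re-scanning to occur every 9 weeks (minus 1-6 days) after initiating protocol treatment on Cycle 1, Day 1". The same note restates the window in cycle days: "re-scanning intended between Days 15-21 of Cycles 3, 6, 9, etc". It then adds: "Same-day scanning on Day 1 of Cycles 4, 7, 10, etc. is discouraged but allowed". Sections 11.1 and 16.1 repeat the 9-week interval.

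**Decision rule (16.211, 16.212).** Stop at 0 of 12; ineffective at 2 or fewer of 21; promising at 3 or more of 21.

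I found no grace period, no statement that the fourth scan belongs to the 36-week endpoint, and nothing that aligns the two clocks. Section 16.23 says only that the last patient must have responded or been followed for 36 weeks.

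**The concern.** Four 9-week intervals make exactly 36 weeks, so the cut-off lands on the fourth scan. That scan is timed from first dose and the cut-off from registration, so the gap between the two dates decides whether the scan counts. Two patients with the same PR on the same on-time fourth scan can be scored differently because one began treatment a week later after registration.

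The rule can be followed without ambiguity. The difficulty is that, followed exactly, it splits one scheduled assessment by administrative timing. In a design where 2 versus 3 of 21 decides the conclusion, a single reclassified patient can matter.

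**Working it through.** **Inputs.** Cut-off: 36 × 7 = 252 days after registration (16.11, 16.21). Start lag L: 0 to 10 days (6.16). Scan interval: 63 days from Cycle 1 Day 1 (4.1, note 5). Cycle length: 21 days.

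**The plan's own timing.** 21 months of accrual plus 252 days (at 30.44 days per month) = 21 + 8.28 = 29.28 months, which agrees with the maximum of 30 months in 16.23.

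**Fourth scan, days after Cycle 1 Day 1.**
- Window of minus 1 to 6 days: 252 − 6 = 246 to 252 − 1 = 251.
- Days 15 to 21 of Cycle 12: 11 × 21 + 14 = 245 to 11 × 21 + 20 = 251.
- Same-day scan on Cycle 13 Day 1: 12 × 21 = 252.

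**Fourth scan, days after registration** = the figure above + L. The range is 245 + 0 = 245 to 251 + 10 = 261, or 252 + 10 = 262 with the same-day option.

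**Number of permitted pre-visit scan days on or before day 252, by lag:**

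| Lag (days) | 0 | 1 | 2 | 3 | 4 | 5 | 6 | 7 | 8 | 9 | 10 |
|---|---|---|---|---|---|---|---|---|---|---|---|
| Minus 1–6 days (of 6) | 6 | 6 | 5 | 4 | 3 | 2 | 1 | 0 | 0 | 0 | 0 |
| Days 15–21 (of 7) | 7 | 7 | 6 | 5 | 4 | 3 | 2 | 1 | 0 | 0 | 0 |

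A same-day Cycle 13 Day 1 scan falls on day 252 + L, so it counts only at lag 0.

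Summing the rows, 66 − 27 = 39 of 66 and 77 − 35 = 42 of 77 combinations of lag and scan day fall after the cut. These count possibilities, with every lag and day weighted equally. They do not forecast how often it will happen.

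**Earlier scans.** On the 9-week calendar the third scan is due by day 189 + 10 = 199 after registration. Scans 1 to 3 therefore always count.

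**How finely the rule is balanced.** At a true response rate of 20%, the probability of passing stage 1 and ending at exactly 3 of 21 is b(21, 3) − b(12, 0) × b(9, 3) = 0.192 − 0.069 × 0.176 = 0.180, where b(n, x) is the binomial probability of x successes in n. In those outcomes one reclassified success reverses the conclusion, but only if that patient first responded at scan 4 and the scan fell after day 252.

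**The case against.** **Registration is a legitimate anchor.** It is used consistently in 16.11, 16.21, 16.311 and 16.321 and for the 3-year follow-up limit in 13.4, and any fixed cut leaves some visits just outside. This stands: the plan contains no error here. What remains is that the cut coincides with a scan timed from another date, and the plan gives no reason for splitting that scan.

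**The consequence is unquantified.** This also stands. Only a first CR or PR at about eight months is exposed. The 0.18 is the chance of sitting on the boundary; the chance that a boundary patient is also lost this way is smaller by an unknown factor. A similar figure for stage 1 would carry little weight, because 16.214 does not suspend accrual. At one patient per month, patient 12 reaches week 36 near month 12 + 8.28 = 20.3, when about 20 patients are already entered.

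**Stronger readings that a reader might infer, and why they fail:**
- *Any start lag loses the fourth scan.* Lags of 2 to 6 days (2 to 7 in cycle days) still leave permitted scan days that count.
- *The fourth scan can run to day 265.* This adds the visit window in note 10, ±3 "days for subsequent study visits is permitted for scheduling considerations other than adverse event management", to a same-day scan that note 5 discourages. Note 10 concerns study visits, and note 5 gives scans their own one-sided window.
- *A lengthened cycle moves the scan further.* The table cell in 4.1 reads "Restaging at end of cycles 3, 6, 9 etc", and section 8.3 allows a cycle to be extended after a hold. But that cell carries note 5 as its footnote, and note 5 counts 9-week intervals from Cycle 1 Day 1. The two wordings should be reconciled, but the cell does not establish a second scan clock.

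**Conclusion.** The point holds as a minor, inexpensive improvement. A fully compliant patient who starts treatment 7 to 10 days after registration (8 to 10 if the window is read in cycle days) cannot have a pre-visit fourth scan inside the endpoint window. At 2 to 6 (or 2 to 7) days the scan day chosen decides, and at 0 to 1 day nothing is lost.

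The conclusion assumes that scans follow the 9-week calendar in note 5 and that the 36-week cut is applied as written.

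A reader might go on to infer that the trial is underpowered or its error rate wrong. The documents do not support that. They give no share of responses first seen at scan 4, and 16.21 sets the 5% and 20% on the registration-anchored proportion itself. The effect can only remove successes, so type I error is not inflated.

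**What to change.** - **16.11, 16.21 (NOTE) and 16.311:** define success as CR or PR up to and including the fourth scheduled restaging, at most 36 weeks (252 days) after Cycle 1 Day 1. This covers every scan that note 5 permits, since these fall on days 245 to 252 after first dose.
- **16.321:** use the same clock for the CR/PR component. Otherwise a first PR on days 253 to 262 after registration would be a success for ORR but not a CR/PR for clinical benefit, although 16.321 says its analysis mirrors the primary one. Leave the 36-week stable-disease minimum unchanged.
- **16.23:** express the 36 weeks of observation on the same clock.
- **4.1:** separately, reconcile the end-of-cycle wording in the CT/MRI cell with its footnote.

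Sample size and cut-offs stay as they are, with no extra scans or patients.

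**Cost.** The window from registration grows by each patient's start lag, at most 10 days. This can only add successes, so the 5% and 20% must be read on the re-anchored proportion, and the protocol should say so. The final analysis moves to 21 months + 262 days = 21 + 8.61 = 29.6 months, within the stated 30. That uses the plan's own 21-month accrual. If all 24 patients projected in 16.22 were entered at one per month, the existing rule would already give 24 + 8.28 = 32.3 months, so that limit is inherited from 16.23 and not created by this change.

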#### 16.2 Statistical Design

##### 16.21 Decision Rule

A Simon two-stage minimax design will be used. The largest success proportion where the proposed treatment regimen would be considered ineffective in this population is 5%, and the smallest success proportion that would warrant subsequent studies with the proposed regimen in this patient population is 20%. The following two-stage design uses 12 or 21 evaluable patients to test the null hypothesis that the true success proportion in this given patient population is at most 5%.

NOTE: We consider a success to be a patient with an objective response by 36 weeks post-registration (i.e. complete response or partial response).

##### 16.211 STAGE 1:

Enter 12 evaluable patients into the study. If 0 successes are observed in the first 12 evaluable patients, we will consider this treatment ineffective in this patient population and terminate this study. Otherwise, if at least 1 success is observed, we will proceed to Stage 2.

**16.212 STAGE 2:**

Enter an additional 9 evaluable patients into the study. If 2 or fewer successes are observed in the first 21 evaluable patients, we will consider this treatment ineffective in this patient population. If 3 or more successes are observed in the first 21 evaluable patients, we may recommend further testing of this regimen in subsequent studies in this population.

**16.213 Over Accrual**

If more than the target number of patients are accrued, the additional patients will not be used to evaluate the stopping rule or used in any decision making process.

**16.214 NOTE:**

We will not suspend accrual between stages to allow the first 12 patients to become evaluable, unless undue toxicity is observed.

**16.22 Sample Size**

The two-stage study design to be utilized is fully described in section 16.21. A minimum of 12 and a maximum of 21 evaluable patients will be accrued onto this study unless undue toxicity is encountered. We anticipate accruing an additional 3 patients to account for ineligibility, cancellation, major treatment violations, or other reasons. Maximum projected accrual is therefore 24 patients. All sample size calculations were computed using PASS 15 software.

**16.23 Accrual Time and Study Duration**

The anticipated accrual rate is 1 patient per month. Therefore, the accrual period for the first stage of this study is expected to be approximately 12 months. If patients are accrued to the second stage, the total accrual period is expected to be approximately 21 months. Should the study continue to full accrual, the final analysis can begin at most 30 months after the trial begins; as soon as the last patient has either responded to therapy, or been observed for 36 weeks.

**16.24 Power and Significance Level**

We assume that the number of successes is binomially distributed, our null success proportion is 0.05, and our alternative success proportion is .20. Given these, along with an assumed type I error rate of 0.1, a sample size of 21 evaluable patients will provide 82% exact power (exact type II error rate = 0.18) to detect a true ORR of 20% or greater (vs. the null hypothesis that the true ORR is at most 5%).

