**16.25 Operating Characteristics**

The probability of declaring that this regimen warrants further studies (i.e. statistical power) under various success proportions and the probability of

stopping accrual after the first stage can be tabulated as a function of the true success proportion as shown in the following table.

If the true success proportion is:	0.05	0.1	0.15	0.2
then the probability of declaring that the regimen warrants further studies is:	0.08	0.35	0.63	0.82
and the probability of stopping at stage 1 is:	0.54	0.28	0.14	0.07

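### The stated 82% exact power and the matching table row ignore the stage 1 stop; the two-stage rule as written has 80.3% power

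*Combined protocol and SAP*

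**What the plan says.** Section 16.21 states the design: "A Simon two-stage minimax design will be used". Stage 1 (16.211) begins: "Enter 12 evaluable patients into the study". If none of the 12 responds, "we will consider this treatment ineffective in this patient population and terminate this study". With at least one response the trial goes on to stage 2 (16.212): "Enter an additional 9 evaluable patients into the study". Three or more responses in 21 may lead to a recommendation for further testing; two or fewer mean the treatment is considered ineffective.

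Section 16.24 gives the hypotheses ("our null success proportion is 0.05, and our alternative success proportion is .20"), the nominal error rate ("along with an assumed type I error rate of 0.1") and the power: "a sample size of 21 evaluable patients will provide 82% exact power (exact type II error rate = 0.18").

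The table in 16.25 Operating Characteristics has two result rows for true success proportions of 0.05, 0.10, 0.15 and 0.20. The row introduced by "then the probability of declaring that the regimen warrants further studies is" reads 0.08, 0.35, 0.63, 0.82. The row for the probability of stopping at stage 1 reads 0.54, 0.28, 0.14, 0.07.

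**The concern.** Under 16.21 the regimen is declared worth pursuing only if two things happen: at least 1 response among the first 12, and at least 3 among all 21. Trials that would have had 0 of 12 and then 3 or more of the next 9 stop early and count as failures. The power must exclude them.

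The printed power row appears to include them, while the row beneath it assumes the stop is enforced. If so, one table describes two different rules, and the headline power and type II error in 16.24 do not belong to the rule that will be applied. These are the only statements of power and operating characteristics for the primary decision, and 16.24 calls them exact. A reader who recomputes the design will not get the published values, and a negative result would be set against a miss probability lower than the true one.

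**Working it through.** **Inputs.** Null and alternative rates 0.05 and 0.20 (16.24); stage 1 size 12, stop at 0 responses (16.211); stage 2 adds 9, total 21, success at 3 or more (16.212). All probabilities are exact binomial, as 16.24 assumes.

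**Step 1: reproduce the printed power row.** With no interim stop, P(success) = P(Bin(21, p) ≥ 3). At p = 0.20:

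1 − [0.8^21 + 21(0.2)(0.8^20) + 210(0.04)(0.8^19)] = 1 − [0.0092 + 0.0484 + 0.1211] = 0.8213.

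The type II error is 0.1787. These round to the printed 0.82 and 0.18. At 0.05, 0.10 and 0.15 the same formula gives 0.0849, 0.3516 and 0.6295, so all four printed entries are reproduced.

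**Step 2: reproduce the stopping row.** P(0 of 12) = (1 − p)^12 = 0.5404, 0.2824, 0.1422, 0.0687. These round to the printed 0.54, 0.28, 0.14, 0.07. This row uses the stop at 0 of 12.

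**Step 3: apply the rule as written.** The two-stage probability is the single-stage probability less the trials that stop at 0 of 12 but would have reached 3 responses in the next 9:

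P(success) = P(Bin(21, p) ≥ 3) − (1 − p)^12 × P(Bin(9, p) ≥ 3).

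At p = 0.20, P(Bin(9, 0.2) ≥ 3) = 0.2618, the subtracted term is 0.0687 × 0.2618 = 0.0180, and the power is 0.8213 − 0.0180 = 0.8033. The type II error is 0.1967.

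| True rate | 0.05 | 0.10 | 0.15 | 0.20 |
|---|---|---|---|---|
| Printed in 16.25 | 0.08 | 0.35 | 0.63 | 0.82 |
| Single stage, 3 or more of 21 | 0.0849 | 0.3516 | 0.6295 | 0.8213 |
| Subtracted term | 0.0045 | 0.0150 | 0.0200 | 0.0180 |
| Two-stage rule as written | 0.0804 | 0.3366 | 0.6095 | 0.8033 |
| Printed minus two-stage, points | 0.0 | 1.3 | 2.05 | 1.7 |

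The 0.05 column cannot tell the two formulas apart, since both values round to 0.08. The other three columns can: each matches the single-stage value and none matches the two-stage value.

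**Step 4: could another design explain both rows?** With 21 patients and a stop at 0 responses, the power row rounds to the printed values only from a stage 1 size of about 16 upwards. At 16 it is 0.0844, 0.350, 0.6275, 0.8197, but the stopping row would then be 0.440, 0.185, 0.074, 0.028. With 22 patients and a stage 1 of 12, power at 20% is 0.8234, but the other entries are 0.0886, 0.3601 and 0.6362, which would print as 0.09, 0.36 and 0.64. Neither alternative gives both rows.

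**Step 5: does the design itself stand?** A search over two-stage designs with type I error at most 0.10 and power at least 0.80 returns 0 of 12 and 2 of 21 as the minimax choice, with actual values 0.080 and 0.803. The design is sound; the reported power is not the design's power.

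**The case against.** The strongest objection is that little turns on this. The design meets 80% power, the type I entry and the stopping row are right as printed, and no interim or final decision would change, because 16.21 decides on fixed counts and 16.312 reports Clopper-Pearson intervals. This stands. It limits the importance of the point, not its correctness.

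A second objection is that the sentence in 16.24, read alone, mentions 21 patients and a binomial count but not two stages, so as a statement about 3 or more of 21 it is exact. That does not help the 16.25 table, where the power row sits directly above the stage 1 stopping row. Nor does it fit 16.22, which refers to the two-stage design when setting the sample size.

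A third is that the stop might not be enforced in practice. Accrual is not suspended between stages (16.214). At 1 patient per month (16.23), about 8 more patients could enter during the 36 weeks after the twelfth (36 × 12/52 ≈ 8.3), so about 20 of 21 might be enrolled when stage 1 is read. If the stop were non-binding, the single-stage figures would be the right ones. But 16.211 says the study ends and the treatment is considered ineffective, nothing calls the rule optional, and continued accrual does not alter the stage 1 verdict.

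Finally, how the figures arose is unknown. Section 16.22 says PASS 15 was used, and its output is not in the document. It can be said only that the printed row equals the single-stage probabilities.

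**Conclusion.** The concern holds. For the rule in 16.21, exact power at a 20% response rate is 80.3%, not 82%, and the type II error is 0.197, not 0.18. The table entries at 10% and 15% should be 0.34 and 0.61, not 0.35 and 0.63. The type I error is 0.080, printed correctly as 0.08.

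This rests on the binomial model in 16.24 and on the stage 1 stop being binding, as 16.211 words it. The error is at most 2.05 points and does not make the trial underpowered against an 80% standard. It is a reporting error in figures labelled exact, and should be corrected because those figures are the plan's only account of how its primary decision rule performs.

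**What to change.** In 16.24, state about 80% exact power, an exact type II error rate of 0.20 and an exact type I error rate of 0.08, and say that these are for the two-stage rule in 16.21.

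In the 16.25 Operating Characteristics table, replace the row for declaring success with 0.08, 0.34, 0.61, 0.80. Leave the stopping row as it is.

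The sample size and the cut-offs (0 of 12, 2 of 21) stay unchanged. The cost is one sentence and one table row, and a stated power that is slightly less favourable.
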